2.6.2 Adjusted analyses

An additional analysis will use GEE as described above and will additionally adjust for appropriate baseline characteristics including gestational age (<27 weeks vs \geq 27 weeks), gender, birthweight (into quartiles), multiple birth (singleton vs multiple birth) and mode of delivery (vaginal versus caesarean). This will only be performed for the primary outcome and death by 24 months.

Table 8: Adjusted analyses for outcomes at 24 months corrected age*

Outcomes at 24 months	ICC n/N (%)	DCC n/N (%)	Relative risk (95% CI)	p-value
Primary outcome:				
Death or major disability*				

Death

*Models are adjusted for gestational age (<27 weeks vs \geq 27 weeks), gender, birthweight (into quartiles), multiple birth (singleton vs multiple birth) and mode of delivery (vaginal versus caesarean).

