3.3 Randomisation

Timing of randomisation

While consent can be attained at any time, randomisation should only take place when delivery is considered inevitable, for example when labour is considered irreversible or when the operating theatre is booked for Caesarean Section and the baby's estimated gestation is less than 30 weeks gestation. Randomisation should be performed allowing sufficient time to use the Interactive Voice Response System i.e. at least ten minutes before the expected birth, or longer than this for multiple births.

Method of randomisation

Randomisation can be done by any member of the obstetric, midwifery, or neonatal team using a phone to call a computerised interactive voice response system.

Randomisation will be performed by using an interactive voice response system built by an independent statistician at the NHMRC Clinical Trials Centre, University of Sydney. All data will be stored securely by the statistical group at the centre.

Randomisation will be by the method of minimisation with two strata: Institution and Gestational age (<27 weeks; >=27 weeks). Multiple births will be randomised separately.

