2 BACKGROUND INFORMATION

Infants born very premature account for approximately 1.5% of live births in Australia,³ but account for a disproportionate burden of disability. Preterm delivery is the primary ascribed cause of death in over 15% of cases of neonatal mortality,³ and very preterm infants develop cerebral palsy around 50 times the rate of infants born at term.⁴ Of infants delivered before 30 weeks gestation, many will develop complications that may be associated with low systemic and organ blood flows during the first 24 hours after delivery, including necrotising enterocolitis (NEC - 7%) and severe (grade 3-4) intraventricular haemorrhage (IVH - 9%).⁵ Mortality rates average from 70% for infants born at 23 weeks to 5% for those born at 29 weeks.⁵ Around 15% of surviving infants born <30 weeks will have a moderate to severe developmental disability resulting in substantial costs to family and society.⁵ Interestingly, delayed cord clamping which has been associated with increased haematocrit in newborn infants, has also been associated with reduced rates of intraventricular haemorrhage and necrotising enterocolitis, both of which are associated with reduced SBF.^{6,7} In addition, use of volume expansion in preterm infants with low SBF was found to increase SBF by a mean of 43%.⁸ It is possible that infants exposed to early cord clamping practices may have a period of unrecognised hypovolemia increasing the risk of low SBF and organ injury. This study aims to evaluate the effect of delayed cord clamping on SBF and organ injuries related to low SBF.

Evidence for hypovolaemia

Hypovolaemia has been reported in newborn infants in the context of fetomaternal haemorrhage, twin-twin transfusion, vasopraevia and antepartum haemorrhage, caesarean section through an anterior placenta and with fetoplacental transfusion resulting from a tight nuchal cord (with the cord cut prematurely to facilitate delivery). However, early hypovolemia has not been thought to contribute to cardiovascular maladaptation in the majority of preterm infants for 2 reasons:

- 1. Studies using labeled albumin have reported that hypotensive preterm infants are not hypovolaemic compared to normotensive infants^{9, 10}, and

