2.4 Delivery and admission characteristics in FU cohort

We will also compare the baseline characteristics of those that are in the FU cohort compared to those that are not in the FU cohort.

Table 4: Patient characteristics at admission and delivery by treatment

	Immediate Cord Clamping Delayed Cord Clampin
N	
Males	
Gestational Age (weeks)*	
Babies <27 weeks gestation*	
Birth details	
Mode of delivery	Vaginal with instruments
	Vaginal without instruments
	Caesarean in labour
	Caesarean not in labour
Presentation at birth	Cephalic
	Breech
	Other (including transverse)
	Unknown
Infants of multiple births	Singletons
(only counting births in the ITT population)	Twins
	Triplets
	Quadruplets
Maternal assessment	
Ethnicity	Caucasian
	Aboriginal/TSI
	Asian
	Pacific Islander & Maori
	Africanŧ
Variables collected pre and po	ost intervention
Uterotonic agents administered	
If yes, what agent?	Syntocin
	Ergometrine
	Carbetocin
	Syntometrin
	Other (including multiple agents)
If yes, what route?	IV
	IM
If yes, timing?	Pre-clamping
	Post-clamping

All characteristics measured prior to intervention were p>0.xx.

*Gestational age is gestational age at birth, as originally specified by the site. Note that reassessed GA has not been used.

+ includes African American. Statistics are given as N (%), mean (SD) or median (Q1-Q3).

August 2020

Page 6 of 17

Page 70 of 81

APTS FU Statistical Analysis Plan v2.2

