2.6 Analysis of outcomes

2.6.1 Primary analyses

The analysis of these outcomes will be a generalised linear model analysis using generalised estimating equations (GEE) with a log link function, and adjusting for multiple births. The estimate of effect will be a relative risk, with a 95% CI.

Analyses of the disability components will be restricted to those that survived to 24 months. A formal analysis will only be performed if there are adequate event numbers (greater than 10 events) at 24 months in each treatment arm.

Table 7: Outcomes at 24 months corrected age, by treatment

	Outcomes at 24 months	ICC n/N (%)	DCC n/N (%)	Relative risk (95% CI)	p-value
	y outcome: or major disability*				
Second	ary outcomes:				
٠	Death				
٠	Major disability*				
٠	Cerebral palsy ⁺				
•	Severe visual loss ⁺				
٠	Deafness ⁺				
٠	Major problems with language/speecht				
•	Cognitive delay ⁺				
with	ajor disability is one or more of the following: (a language or speech or cognitive delay. ese analyses are restricted to those that were				najor proble

August 2020

Page 9 of 17

Page 73 of 81

APTS FU Statistical Analysis Plan v2.2

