2.6.4 Multiple imputation analysis

A multiple imputation analysis^{1,2,3} using chained equations⁴ will be conducted for the primary outcome as a sensitivity analysis. Covariates to be included in both the imputation stage and the modelling stage include: treatment, gestational age (<27 weeks vs \geq 27 weeks), gender, birthweight (into quartiles), multiple birth (singleton vs multiple birth) and mode of delivery (vaginal versus caesarean).

August 2020

Page 12 of 17

Page 76 of 81

APTS FU Statistical Analysis Plan v2.2

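### The adjusted and imputation models use gestational age only as a 27-week split, although week of gestation is collected, so the supporting relative risks are slightly less precise than they could be

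*Supplement*

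**What the plan says.** The primary analysis (SAP v2.2, 2.6.1) uses "generalised estimating equations (GEE) with a log link function, and adjusting for multiple births". It has no gestational age term.

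The adjusted analysis (2.6.2) "will additionally adjust for appropriate baseline characteristics including gestational age (<27 weeks vs" 27 weeks or more. The other covariates are gender, quartiles of birthweight, singleton or multiple birth, and vaginal or caesarean delivery. The analysis covers only the primary outcome and deaths up to 24 months.

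The imputation (2.6.4) repeats the coding: "Covariates to be included in both the imputation stage and the modelling stage include: treatment, gestational age (<27 weeks vs" 27 weeks or more. The other terms are the same as in 2.6.2.

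The Cox model (2.6.5) is adjusted for gestational age, but the form is not stated.

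Protocol v4.0, section 3.3, balances on the same cut: "Randomisation will be by the method of minimisation with two strata: Institution and Gestational age (<27 weeks; >=27 weeks".

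The finer information exists. SAP Table 4 has a row labelled "Gestational Age (weeks", and its footnote says "Gestational age is gestational age at birth, as originally specified by the site". The echocardiography sub-study protocol (section 2) gives the gradient: "Mortality rates average from 70% for infants born at 23 weeks to 5% for those born at 29 weeks".

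**The concern.** Allocation was already balanced, approximately, on the 27-week cut. The chance imbalance that remains in maturity lies between weeks inside each stratum, for example 23 against 26 weeks, and a two-level term cannot see it. Birthweight quartiles are the only listed covariate that follows week closely within a stratum, and they do so imperfectly. Birth weight is also a tertiary outcome in Protocol v4.0 (3.4.5), whereas the timing of clamping cannot change the week of gestation.

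In the imputation, a 23-week and a 26-week infant with missing outcome share one gestation term. If both follow-up and outcome vary by week within the strata, missing at random given the listed covariates is harder to defend than the collected data require.

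At stake are the precision of the adjusted relative risks for the primary outcome and for death, and the credibility of the imputation as a sensitivity analysis.

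**Working it through.** **The plan's own figure.** The plan gives no figure on this point. The nearest is SAP Table 1: 80% power with 1,350 infants for 35% against 25% with 30% non-compliance. The diluted difference is 0.70 × 10 = 7 points. Two-sided 0.05 with 675 per arm gives 79.1% power for 35% against 28% (all dilution in the deferred arm), or 80.2% for 33.5% against 26.5% (15% in each arm). The stated 80% reproduces and is not in dispute.

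**Inputs.**
- Mortality of 70% at 23 weeks and 5% at 29 weeks (sub-study background).
- Follow-up cohort of 1,531 (SAP 2.6.3.2).
- Composite rate of 35% (SAP Table 1).
- Share below 27 weeks: 534/1,600 = 33%, and mortality of 10%. Both come from the sample-size text of a superseded protocol version and serve only as assumptions.
- Assumed: interpolation linear on the logit scale, and a week mix for 23 to 29 weeks of 2, 7, 10.5, 14, 18, 22 and 26.5%.

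**Gradient inside the strata.** The slope is (logit 0.05 − logit 0.70)/6 = (−2.944 − 0.847)/6 = −0.632 per week. Mortality for weeks 23 to 29 is then 70, 55, 40, 26, 16, 9 and 5%. It runs from 70% to 26% below 27 weeks and from 16% to 5% at 27 weeks or more.

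**What the cut keeps.** Let q be the share and m the mortality in each week.
- Overall mean μ = Σqm = 0.192, so the total variance is 0.192 × 0.808 = 0.155.
- Stratum means are 0.390 (share 0.335) and 0.092 (share 0.665).
- Variance explained by the cut: 0.335 × 0.198² + 0.665 × 0.100² = 0.0198, so R² = 0.128.
- Variance explained by week, Σq(m − μ)², gives R² = 0.175.
- Share kept by the cut: 0.128/0.175 = 73%. Over three interpolations and three week mixes the range is 62–77%.
- With birthweight quartiles added (assumed correlation with gestation 0.6–0.8): 64–82%.

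So 18–36% of the between-week mortality variance stays unmodelled under the planned covariates.

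**What that costs.** For a linear model on the risk-difference scale, with quartiles at correlation 0.7 (R² 0.133), the variance ratio is (1 − 0.133)/(1 − 0.175) = 1.05. This takes the 70% and 5% at face value, which implies 19% overall mortality, well above 10%. The SAP reports relative risks, so the loss was also simulated on that scale. The settings were 3,000 trials per scenario, 1,531 infants, allocation balanced on the cut, true RR 0.85, a Poisson working model with log link, and birthweight correlated 0.7 with gestation. The intercept was shifted to give the stated control rate. Entries are the SD of the log RR; ratios come from unrounded SDs.

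| Scenario | Unadjusted | Cut | Cut + quartiles | Same + weeks | Variance ratio, last two |
|---|---|---|---|---|---|
| Death 10% | 0.1570 | 0.1570 | 0.1566 | 0.1541 | 1.033 |
| Composite 35%, mortality slope on all of it | 0.0700 | 0.0700 | 0.0697 | 0.0688 | 1.028 |
| Composite 35%, slope on death only, disability flat at 0.25/0.90 of survivors | 0.0761 | 0.0761 | 0.0760 | 0.0760 | 1.002 |

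Two further runs under other assumptions compared a model in weeks with the cut plus quartiles. For the composite with the full slope they gave (0.0664/0.0652)² and (0.0654/0.0641)², both about 1.04. For death, one gave (0.1577/0.1543)² = 1.045 and the other 1.5–2%.

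The cut alone gains nothing over no adjustment in any scenario. Adding weeks gains about 2–4% of variance for death. For the composite it gains up to about 4%, and 1% or less if disability does not vary by week.

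**The case against.** The strongest case against is that this cannot change the trial's conclusion. Section 2.6.2 is an additional analysis and 2.6.4 a sensitivity analysis, the cut is prespecified, and it matches both the minimisation factor and the subgroup. That stands, and it fixes the weight of the point.

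Several stronger readings are tempting but unsupported:
- A reader might infer that the gradient within strata is left untouched. It is not: birthweight quartiles recover a little of it.
- A reader might put the loss at about 6% of variance, or some 85 infants (0.056 × 1,531 = 86). That compares weeks with the cut alone, which is not the planned model, and it applies the mortality slope to the whole composite. The documents give a gradient for mortality only.
- A reader might call adjustment for the cut a mistake. It is proper to keep a minimisation factor in the model. Balance is also only approximate: allocation preceded birth, the model uses gestation at birth, and infants are excluded after randomisation.
- A reader might infer that the imputed results are biased. The documents give no missingness by week and no disability rate by week, so neither the direction nor the size can be stated.

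A log-link model can also fail to converge once a continuous covariate is added at high risks. That is a fair practical objection, and the fix allows for it.

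**Conclusion.** The point holds as a minor one. Both supporting models use only the cut that minimisation had already used, and no model in the SAP is stated to use week of gestation, although it is collected and strongly prognostic for death. The adjusted relative risks lose roughly 1–4% of variance (about 0.5–2% of the standard error), and less than 1% for the composite if disability is flat by week. These figures rest on an assumed week mix, an interpolation between two documented end points, an assumed correlation of birthweight with gestation, and an undocumented disability gradient. No bias is shown. The imputation point is sound in principle but cannot be sized. The primary GEE of 2.6.1 is not affected.

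**What to change.** In 2.6.2 and 2.6.4, add gestational age at birth in weeks (linear plus quadratic, or a spline) alongside the two-level minimisation factor, and change the Table 8 footnote to match. State the same form for the Cox model in 2.6.5. Name a modified-Poisson model with robust variance, still accounting for multiple births, as the fallback if the log-link model does not converge. Keep the 27-week cut for the subgroup analysis in 2.7.

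The cost is a short SAP edit, one or two more parameters (a few for a spline), and possible use of the fallback. No new data are needed, and the treatment effect is still reported as a relative risk.

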2.6.3 Treatment adherence weighted analysis

The primary outcome will also have the following treatment adherence weighted analyses performed.

2.6.3.1 Simple weighted approach

Firstly, an overall treatment adherence adjusted estimate will be calculated. This will be calculated using a simple weighting of the overall estimate of relative risk reduction (RRR):

 $RRR_{\text{adjusted}} = \frac{RRR}{100 - (\text{non compliance}^{(\text{ICC})} + \text{non compliance}^{(\text{DCC})})}$

Where

RRR is the relative risk reduction (%) for the primary outcome (Table 7) non compliance^(ICC) is the treatment non-adherence percentage for ICC in Table 3 non compliance^(DCC) is the treatment non-adherence percentage for DCC in Table 3

2.6.3.2 Weighted subgroups by treatment adherence approach

Additionally, a weighted average approach, weighting by measures of treatment received will be undertaken, following the same principles used in the APTS main study analyses, while preserving the effect of randomisation. In these planned analyses we propose the following two approaches:

(a) sites which enrolled 50 or more babies will be considered a cluster and sites with less than 50 babies will be amalgamated to make a cluster of over 50 with other sites in the same geographic area;

(b) sites which enrolled 10 or more babies will be considered a cluster and amalgamated into a cluster with sites with less than 10 babies will be amalgamated with others in the same geographic area to form another 'cluster' with 10 or more babies (as shown in Table 9).

August 2020

Page 10 of 17

Page 74 of 81

APTS FU Statistical Analysis Plan v2.2

These clusters are slightly different from those proposed in the main paper as we have fewer patients with the follow-up component of APTS (1531 vs 1566), and also fewer with complete data at 2 years. Analysis (b), in which sites of 10 or more babies will be considered a 'cluster' as per Table 9, will allow us to assess the effect of placing less emphasis on the arbitrary grouping of sites by geographical location in analysis (a).

The main measure to be used to estimate treatment adherence will be the mean difference in clamp time (in seconds) between the ICC and DCC arms. Additional measures to be investigated include:

- mean clamp time in seconds in the DCC arm only
- proportion of compliant babies, where compliant is <10 seconds and not milked versus >=60 seconds and not milked
- proportion of babies who are compliant in the DCC arm only (>=60seconds and not milked)

For each measure of treatment adherence, the average for each treatment in each cluster will be calculated. For some measures, the difference between the two treatments will be calculated while for others, the measure of treatment received in the delayed clamping arm alone will be used. This value will then be used to rank the (a) 15 and (b) 22 clusters (as below in Table 9) for increasing adherence to protocol. These clusters in (a) and (b) will be grouped into 3 sets according to adherence to protocol, i.e. (a) 5 'low', 5 'medium' and 5 'good' adherence to protocol treatment (total 15 clusters) or (b) 7 'low', 8 'medium' and 7 'good' adherence to protocol treatment (total 22 clusters).

The main measure to be used to estimate treatment adherence will be the mean difference in clamp time (in seconds) between the ICC and DCC arms. For example, if all babies in the control group complied with the protocol specifications we might expect an average clamp time to be 5 seconds, whereas in the delayed arm, the average time would be 60 seconds, so the achieved difference would be 55 seconds. The value of the treatment adherence to be used for that cluster would be 55.

For each measure of treatment adherence, a weighted analysis will be carried out to obtain an estimate of the effect of the intervention, weighted by the degree of treatment adherence. An estimate of the achieved effect of delayed cord clamping, for each of the 3 groups of clusters, will be obtained from a generalised linear model. A weighted average of the treatment adherence for each group will be calculated using a weighted average of the values for each cluster. Finally, an estimate of the effect of the intervention weighted for non-adherence will be derived by a weighted average of the 3 group estimates.

The details of the method are in Appendix One.

August 2020

Page 11 of 17

Page 75 of 81

APTS FU Statistical Analysis Plan v2.2

Table 9: Listing of sites within each cluster

25 APTS sites	15 clusters, obtained from individual sites with ≥50 patients or by amalgamating sites with <50 patients with others by geographic area	22 clusters, obtained from individual sites with ≥10 patients or by amalgamating 3 sites with <10 patients with others by geographic area
Aga Khan University	Pakistan	Pakistan
Hopital Antoine Beclere	France/N America	France
Fletcher Allen Health Care Medical Center Texas Children's Hospital IWK Health Centre		N America
Royal Jubilee Maternity Hospital Craigavon Area Hospital	Northern Ireland	Northern Ireland
Royal Hospital for Women	NSW and ACT	Royal Hospital for Women
Canberra Hospital		Canberra Hospital
Liverpool Hospital		Liverpool Hospital
Royal North Shore Hospital	RNS hospital	RNS hospital
Royal Prince Alfred Hospital	RPA hospital	RPA hospital
John Hunter Hospital	John Hunter	John Hunter
Mater Mothers Hospital	Queensland	Mater Mothers Hospital
Royal Brisbane and Women's Hospital		RBWH
Townsville Hospital		Townsville Hospital
Mercy Hospital For Women	Melbourne	Mercy Hospital For Women
Monash Medical Centre		Monash Medical Centre
Flinders Medical Centre	Flinders	Flinders Medical Centre
King Edward Memorial Hospital	KEMH	King Edward Memorial Hospital
Waikato Hospital	NZ	Waikato Hospital
Dunedin Hospital		Dunedin Hospital
Auckland Hospital	Auckland	Auckland Hospital
Christchurch Hospital	Christchurch	Christchurch Hospital
Wellington Hospital	Wellington	Wellington Hospital

2.6.4 Multiple imputation analysis

A multiple imputation analysis^{1,2,3} using chained equations⁴ will be conducted for the primary outcome as a sensitivity analysis. Covariates to be included in both the imputation stage and the modelling stage include: treatment, gestational age (<27 weeks vs \geq 27 weeks), gender, birthweight (into quartiles), multiple birth (singleton vs multiple birth) and mode of delivery (vaginal versus caesarean).

August 2020

Page 12 of 17

Page 76 of 81

APTS FU Statistical Analysis Plan v2.2

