3.4 Endpoints

3.4.1 Primary outcome

Death and/or major morbidity at 36 completed weeks post menstrual age.

Morbidity is defined by one or more of the following obtained from the medical record:

- Brain injury on ultrasound
- Severe retinopathy
- Necrotising enterocolitis
- Late onset sepsis

Page 25 of 81

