2.5 Outcome definitions

The primary outcome is death and/or major disability at 24 months corrected age. Assessments of major disability must be performed between 18 months to 27 months. Any data outside of this window will require a central review.

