Major problems with language or speech	Tier 1: SHSQ completed between 22-27 months (inclusive)	Unable to speak 10 words	Able to speak >10 words
	Tier 2: ASQ-3 completed after 18 months	Communication score indicative of delay (based on published ASQ cut-off)	Communication score not indicative of delay (based on published ASQ cut-off)
	Tier 3: Central review		
Cognitive delay	Tier 1: ASQ-3 completed after 18 months	Problem solving score indicative of delay (based on published ASQ cut-off)	Problem solving score not indicative of delay (based on published ASQ cut-off)
	Tier 2: Central review		

⁺ the windows given above for the determination of disability using the various sources were determined by clinicians involved in the APTS Follow-up study. All ages are corrected ages.

If the baby is alive and does not have one of the above major disabilities, and has been assessed for all of the above components, then they will be classified as alive and disability free. If the infant was alive and has no disability for CP, severe visual loss, deafness and major problems with language or speech, but missing information for cognitive delay, then the infant will be assumed to be alive and disability free at 2 years. Otherwise the infant will be considered as missing for the primary analysis.

Page 8 of 17

Page 72 of 81

APTS FU Statistical Analysis Plan v2.2

Table 6: Summary of completeness of the primary outcome and its components

Endpoint	Complete data	Missing data
Death or disability at 24 months		
Death status		
Cerebral palsy ⁺		
Severe visual loss+		
Deafness [†]		
Major problems with language or speech ⁺		
Cognitive delay ⁺		
hese analyses are restricted to those that were as	ssessed for these outcon	nes

Additionally, the baseline characteristics will be compared between those that have outcome data at 24 months versus those that have missing data at 24 months.

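### As listed, the multiple imputation nearly repeats the adjusted complete-case analysis, and no planned analysis of the primary outcome departs from missing at random

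*Supplement*

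**What the plan says.** The follow-up SAP (v2.2, section 2.5) sets the endpoint: "The primary outcome is death and/or major disability at 24 months corrected age". Section 2.5.2 classes a survivor with four negative components and no cognitive result as disability free. For other infants who cannot be classified it says: "Otherwise the infant will be considered as missing for the primary analysis". The primary analysis is therefore complete-case. Section 2.6.1 specifies it as a "generalised linear model analysis using generalised estimating equations (GEE) with a log link function, and adjusting for multiple births", with no other covariates.

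Section 2.6.2 adds an adjusted version (Table 8) with gestation below or above 27 weeks, "gender, birthweight (into quartiles), multiple birth (singleton vs multiple birth) and mode of delivery (vaginal versus caesarean").

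Section 2.6.4 states that a multiple imputation by chained equations "will be conducted for the primary outcome as a sensitivity analysis". On its content it says: "Covariates to be included in both the imputation stage and the modelling stage include: treatment, gestational age", and then gives the rest of the 2.6.2 list. It does not say whether the composite or its components are imputed, and it names no variable outside that list. No delta-adjusted or other missing-not-at-random analysis appears in the SAP.

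**The concern.** A sensitivity analysis for missing outcomes is useful if it brings in information that the main analysis leaves out, or if it changes the assumption about the missing infants. As listed, this one does neither relative to Table 8. The risk is in interpretation: Tables 7 and 8 and the imputation may agree closely, and a reader may take that as three-way support when the last two share the same assumption and nearly the same information.

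This matters because SAP 1.5 allows for up to 150 infants lost, the trial is open label, and part of the disability assessment is by parent report. Loss or non-response that differs by arm and by the child's condition cannot be excluded.

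**Working it through.** **The plan's own figure.** The only related number is the power in SAP Table 1. Diluting 35% to 25% by 30% non-compliance gives a difference of 10 × 0.70 = 7 points, so 35% against 28%. With 675 per arm at two-sided 0.05, power is 79.1%. All six rows give 78.6% to 79.3%, consistent with the stated 80%. Nothing below depends on it.

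**Amount missing.** The cohort is 1,566 − 35 = 1,531 (SAP 2.2 and 2.6.3.2). The maximum planned loss is 150/1,531 = 9.8%. The 20% scenario below is an assumption.

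**Structure.** Write Y for the composite and X for treatment plus the listed covariates. If only Y is missing, an infant with X but no Y carries no information about Y given X. Imputation draws Y from the model for Y given X fitted to the complete cases. Refitting a model on the same X and pooling then returns the complete-case coefficient, apart from simulation noise and any small mismatch between imputation and analysis links.

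**Simulation.** N = 1,531; loss among survivors only; 20 logistic imputations of the composite on the SAP list; log-link Poisson analysis with robust standard errors; 60 replicates per row. Prevalences, effects and loss mechanisms are assumed, and clustering within multiple births was not modelled. Entries are relative risks (geometric means over replicates). The last column adds a 36-week morbidity indicator and fits the imputation model in survivors.

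| Missing | Loss depends on | Full data | Adjusted complete-case | Imputation, SAP list | Imputation with auxiliary, survivors |
|---|---|---|---|---|---|
| 10% | listed covariates | 0.869 | 0.868 | 0.868 | 0.870 |
| 10% | morbidity, by arm | 0.918 | 0.917 | 0.917 | 0.922 |
| 10% | disability, both arms | 0.895 | 0.893 | 0.892 | 0.894 |
| 10% | disability, deferred arm only | 0.891 | 0.836 | 0.838 | 0.834 |
| 20% | listed covariates | 0.888 | 0.884 | 0.886 | 0.886 |
| 20% | morbidity, by arm | 0.894 | 0.888 | 0.889 | 0.895 |
| 20% | disability, both arms | 0.915 | 0.909 | 0.908 | 0.911 |
| 20% | disability, deferred arm only | 0.877 | 0.787 | 0.787 | 0.781 |

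- Mean absolute gap in log RR between the SAP-list imputation and the adjusted complete-case fit: 0.005 to 0.009. Standard errors are 0.09 to 0.10 for both.
- Gap to the unadjusted complete-case fit: 0.018 to 0.030. This is the effect of covariate adjustment, which Table 8 already shows.
- One-arm loss tied to disability: ln(0.838/0.891) = −0.061 at 10% and ln(0.787/0.877) = −0.108 at 20%. The imputation shares this bias with the complete-case fit.
- Adding the auxiliary and restricting to survivors moves the estimate by only 0.007 to 0.015 from the adjusted complete-case fit, and does not remove that bias.

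A separate simulation of 150 trials with 9% of survivors missing gave mean RR 0.849 (imputation) and 0.848 (complete-case), standard error 0.078 for both, and a correlation of 0.998 between the estimates.

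**Survivors.** Assume a 31% composite of which 9 points are deaths, and 9% of survivors lost at random. Disability among survivors is 0.22/0.91 = 24%. A composite model fitted with the deaths imputes about (0.09 + 0.22 × 0.91)/(0.09 + 0.91 × 0.91) = 0.2902/0.9181 = 32%. The effect on the relative risk is small. With 9% deaths in both arms and composites of 34% and 28%, the observed risks are 0.3175/0.9181 and 0.2629/0.9181. Their ratio is 0.828 against a true 0.28/0.34 = 0.824, a gap of about 0.005 on the log scale.

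**The case against.** Several stronger readings are tempting, and the documents do not support them.

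- *That the imputation certainly imputes the composite on a closed list.* Section 2.6.4 names the primary outcome, which 2.5 defines as the composite, but it does not say that components are left out. Chained equations are often used for several incomplete variables, Table 6 tracks each component, and the verb introducing the covariates need not be exhaustive. Both points are inferences. If components are imputed, partial data would add some information.
- *That it reproduces the primary result.* It matches Table 8. Against the GEE of 2.6.1 it does address loss related to the listed baseline factors, although 2.6.2 already does so.
- *That the plan tests nothing about missing data.* Section 2.5.2 compares baseline characteristics by outcome availability, section 2.4 compares infants in and out of the follow-up cohort, and the tiers and blinded central review reduce missingness. These steps are worthwhile, but they do not show how the relative risk would change if the missing infants differed.
- *That all missing infants are survivors.* Section 2.5.1 counts as alive only those known alive at 21 months or later. An infant lost after discharge may have died, so some risk of death belongs in the imputation.
- *That much partial information is discarded.* One positive component settles the composite, and four negatives with cognition missing are classified. What remains unused is negative components where another non-cognitive item is missing.
- *That the planned result is biased.* The simulation shows what one-arm loss could do. It is not evidence that such loss occurred.

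What remains is that the listed model adds almost nothing to Table 8, and the missing-at-random assumption is never varied.

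**Conclusion.** The point holds in limited form. With the list in 2.6.4 and an imputed composite, the imputation should agree with the adjusted complete-case analysis to within about 0.01 in log relative risk, roughly a tenth of a standard error. It would differ from the primary GEE only through covariate adjustment. The near-identity follows from the model structure and does not rest on the simulated rates. The size of any bias under informative loss does rest on them, and is shown only as a possibility.

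Agreement among these analyses should not be reported as robustness to missing outcomes. The primary analysis itself is unaffected, so this is a worthwhile improvement to a sensitivity analysis and not a flaw in the main result.

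**What to change.** 1. **Main change.** Add a delta-adjusted (tipping-point) analysis by arm for infants with a missing primary outcome. Vary the imputed risk separately in each arm and report where the conclusion would change.
2. **State what is imputed, and condition on known survival.** Infants known to be alive at the 24-month landmark should be given a risk of disability only. Infants whose 24-month survival is unknown should keep some risk of death.
3. **Add auxiliary predictors already collected.** These are the 36-week morbidities (Protocol V4.0, 3.4.1: "Morbidity is defined by one or more of the following obtained from the medical record"), including brain injury, with chronic lung disease from 3.4.3; observed disability components and ASQ-3 or Bayley-III results; and site or the site clusters of SAP Table 9. Site is relevant because Protocol V4.0, 8.1, expected some regions to fall outside extended follow-up.
4. **Analyse the imputed data with the primary GEE of 2.6.1**, so that the comparison is with the primary result. Where individual components are too rare for stable models, impute disability status as one variable.

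The cost is analyst time, with no new data collection. Steps 2 and 3 are expected to move the relative risk little, so step 1 should not be dropped in their favour.
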